### **15.3.2 Clinical Laboratory Results**

Normal ranges will be used to identify values that are outside the normal ranges and abnormal laboratory results will be graded according to the NCI CTCAE v4.0.

A shift summary of baseline grade by maximum post-baseline CTCAE grade will be presented, as appropriate. For each laboratory parameter, the baseline laboratory value will be defined as the last laboratory value collected on or prior to the date of the first dose of study drug.

Patients who develop toxicities of Grade  $\geq 3$  will be summarized. Laboratory test results not having CTCAE grade will also be summarized. Parameters that have criteria available for both low and high values (e.g., hypercalcaemia vs. hypocalcaemia) will be summarized for both criteria. Patients will only be counted once for each criterion.

### **15.3.3 Vital Signs**

Each vital sign (temperature, blood pressure [systolic and diastolic], respiration rate, and heart rate) will be summarized and presented by study visit. Patients with clinically significant abnormalities in vital signs as compared to baseline will be listed.

### **15.3.4 Concomitant Medications/Treatments**

All medications and/or treatments received during the protocol treatment period will be considered as concomitant medications and/or concomitant treatments and will be coded by medical dictionary; patients who received concomitant medications and/or treatments will be listed.

### **15.3.5 Endometrial Thickness**

Endometrial thickness changes during study as compared to baseline will be summarized and presented by study visit.

### **15.3.6 Ventricular Repolarization**

Standard ECG intervals RR and QT will be determined for each ECG recording. Corrected QT intervals (QTc) will be determined using Fridericia's formula. Changes in ECG intervals from baseline will be calculated. Baseline is defined as either the single ECG measurement (Phase I) or the mean of the triplicate ECG measurements (Phase II) collected during screening. Standard evaluation procedures will be employed in the reading of the ECGs.

Tables to be prepared include analysis of time-matched mean differences between baseline and postdose assessments, and analysis of maximum change from baseline for each patient.

In addition, patient's QTc (Fridericia) will be categorized based on ICH E14 guidance. Tables will present the number and percentage of patients meeting or exceeding the following categories:

#### **QTc interval prolongation**

Absolute values  $>450$  to  $\leq 480$  msec

Absolute values  $>480$  to  $\leq 500$  msec

Absolute values  $>500$  msec

#### **QTc interval change from baseline**

Increase from baseline  $>30$  to  $\leq 60$  msec

Increase from baseline  $>60$  msec

### **15.4 PHARMACOKINETIC ANALYSES**

For PK analyses, the analysis population will consist of the subset of treated patients who have at least one PK sample collected.

During the Phase Ia *portion of the study*, full plasma PK profiles will be obtained for GDC-0810 and its glucuronide metabolites, and analyzed using non-compartmental methods for all patients in the dose escalation portion of the study.

In the Phase IIa portion of the study, full plasma PK profiles will be obtained for GDC-0810 and analyzed using non-compartmental methods.

In the Phase Ib portion of the study, full plasma PK profiles will be obtained for GDC-0810 and palbociclib and/or LHRH agonists and analyzed using non-compartmental methods.

In addition, in the Phase Ia/IIa/Ib, blood samples for determination of the steady-state trough concentrations (predose) of GDC-0810 will be *obtained from* all patients.

### **15.5 ANTI-TUMOR ACTIVITY**

Objective response and clinical benefit rates will be derived according to RECIST v1.1 and summarized by dose level and cohort. Progression-free survival will be listed for all patients in Phase IIa, when appropriate.

Objective response is defined as a complete response or partial response, as determined by investigator assessment and confirmed by repeat assessment  $\geq 4$  weeks after initial documentation. Patients with missing baseline or no response assessments will be classified as non-responders.

CBR is defined as the percentage of patients achieving confirmed RECIST v1.1-defined complete response, partial response, and/or stable disease  $\geq 24$  weeks.

Progression-free survival is defined as the time from the first day of study treatment with GDC-0810 in the Phase IIa until documented disease progression or death, whichever occurs first. For patients who do not have documented progressive disease or death before the end of the study or who are lost to follow-up, progression-free survival will be censored at the day of the last tumor assessment.

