##### **Phase IIa**

Disease assessments (CT scan of the chest, abdomen, and pelvis, plus a bone scan) will be performed at screening and every 8 weeks from Cycle 1 Day 1 thereafter, regardless of treatment delays resulting from toxicity. Radiographic confirmation of objective tumor response or disease progression will be based on RECIST v1.1.

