#### **6.1.2 Phase IIa**

- To determine the anti-tumor activity of single agent GDC-0810 in postmenopausal women with locally advanced or metastatic ER+ (HER2-) breast cancer

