### **11.1.8 Tumor Assessments**

Disease assessments will be performed at screening, *per institutional guidelines, and as clinically indicated*.

Imaging studies will include a CT scan of the chest, abdomen, and pelvis, plus a bone scan. At screening, a CT/MRI brain should be obtained if clinically indicated to rule out newly diagnosed, untreated brain metastasis.

Radiographic confirmation of objective tumor response or disease progression will be based on RECIST v1.1 ([Eisenhauer et al. 2009](#)).

The same method of assessment and the same technique should be used at screening and during follow up. Intravenous (IV) contrast is required when not medically contraindicated. Patients who have a contraindication to IV contrast may have MRI exams of the abdomen and pelvis performed in lieu of CTs and a non-contrast CT of the chest. Tumor evaluation by PET scan or by ultrasound may not substitute for CT or MRI scans. However, a CT for tumor assessment may be acquired on a PET/CT scanner if it is of full diagnostic quality and includes IV contrast.

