### **15.1 PLANNED ANALYSES**

Planned analyses include the analyses of safety, PK, anti-tumor activity, and data from the FES-PET imaging correlative studies.

Due to the exploratory nature of this study, no confirmatory inferential analyses are planned, and no imputation for missing data will be done. Descriptive statistics (such as means, medians, standard deviations, and ranges for continuous data and percentages for categorical data) will be used to summarize patient characteristics, treatment

administration/compliance, safety parameters, pharmacokinetic parameters, anti-tumor activity endpoints, and exploratory biomarkers. Data will also be displayed graphically, where appropriate. Baseline values will be defined as the closest measurement prior to the first dose of study drug, typically those collected during screening. Change from baseline will be defined as (post-baseline value – baseline value). Data will be summarized by phase/stage and dose cohorts.

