## Appendix 2 Schedule of Activities: Phase IIa

Protocol Activities	Screening	Cycle 1	Cycles 2+ [1]		End of Treatment [2]	Safety Follow-Up (+ 2 days) [3]
	≤ 28 days of 1 st dose	Day 1	Labs Biopsies, scans			
Baseline Documentation						
Informed Consent	X					
Medical/Oncological History [4]	X					
Physical Examination [5]	X	X	X		X	(X)
CT/MRI Brain [6]	X					
Laboratory Studies						
Hematology and Blood Chemistry [7]	X	X	X [1]		X	(X)
Urinalysis [7]	X		X		X	
Circulating tumor DNA [7]	X		C3 only		X	
Pharmacogenomic sample [7]		X				
Trough PK Sample [8]		X	X (only Cycles 3, 4)			
GDC-0810 Dosing [9]		X→	X→			
Triplet 12-Lead ECG [10]	X		Cycle 2 Day 1 predose and at 1, 2, 3, 4, 6 hours		X	
PK Sample [11]			Cycle 2 Day 1 predose and at 1, 2, 3, 4, 6 hours following dosing			
Efficacy/PD Assessments						
CT/MRI Chest, Abdomen, Pelvis [12]	X		X		X	
Bone Scan [12]	X		X		X	
FES-PET/CT Scan (Cohort A1 patients) Collect E2 and SHBG samples prior to performing the scan [13]	X		C3 and whenever disease progression is suspected			

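### Phase IIa progression-free survival is defined with censoring but only listed, and its censoring rule gives a time of zero or less for a patient with no post-baseline scan

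*Combined protocol and SAP*

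**What the plan says.** Section 15.5 (Anti-Tumor Activity) treats its measures differently. Objective response and clinical benefit rates are to be summarised by dose level and cohort. For PFS the commitment is "Progression-free survival will be listed for all patients in Phase IIa, when appropriate". The closing qualifier is not defined, and no survival method is named anywhere in the document.

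The clock starts at first dose: "Progression-free survival is defined as the time from the first day of study treatment with GDC-0810 in the Phase IIa", running to documented progression or death. For patients without either, or lost to follow-up, "progression-free survival will be censored at the day of the last tumor assessment". Section 15.5 counts patients with no response assessments as non-responders for objective response. It gives no matching rule for PFS.

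Section 15.1 says descriptive statistics will summarise a list of items ending "administration/compliance, safety parameters, pharmacokinetic parameters, anti-tumor activity endpoints, and exploratory biomarkers". The statistics it names as examples are means, medians, standard deviations and ranges for continuous data, and percentages for categorical data.

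On scan timing, Section 11.1.8 begins "Disease assessments will be performed at screening" and then defers to institutional guidelines and clinical indication. The Phase IIa schedule in Appendix 2 sets the screening window as "≤ 28 days of 1 st dose".

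The Phase IIa primary objective (Section 6.1.2) is "To determine the anti-tumor activity of single agent GDC-0810 in postmenopausal women". PFS is not mentioned there or in any other objective.

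**The concern.** Two things look wrong. First, a measure with a full censored-data definition has no analysis that uses the censoring. If the Section 15.1 statistics were applied to it, a patient censored while progression-free would count as if she had progressed on that day. Second, the censoring date can fall before time zero, because for some patients the last tumor assessment is the screening scan.

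At stake is a usable supportive reading of anti-tumor activity in a single-arm expansion. Clinical benefit rate needs a full 24 weeks of stable disease, or a confirmed response, and Section 15.5 does not say how it treats a patient who is progression-free with shorter follow-up. A Kaplan-Meier estimate uses that partial follow-up. Section 2.2 also reports external results as median PFS with confidence intervals, for example 3.8 months (95% CI 3.5 to 5.5) in the fulvestrant-plus-placebo arm of a Phase III study. A listing gives no corresponding estimate.

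**Working it through.** **1. The plan's own precision figures.** There are none for PFS. Table 13 covers only response rate (Cohort A) and clinical benefit rate (B1, B2). Exact (Clopper-Pearson) 80% limits are the 0.10 quantile of Beta(x, n-x+1) and the 0.90 quantile of Beta(x+1, n-x):

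- A, 5/30: 8.34% to 28.74%
- B1, 25/50: 40.09% to 59.91%
- B2, 4/20: 9.02% to 36.07%

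All three match Table 13. The Cohort A row is labelled 15% but reproduces with 5/30 = 16.7%.

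**2. Sections 15.5 and 15.1 side by side.** The specific text lists PFS. The general text summarises anti-tumor activity endpoints, which on its face can include PFS, but with statistics that ignore censoring. On either reading there is no valid time-to-event summary.

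**3. The censoring date.** PFS time = censoring date minus first-dose date. If the only scan was s days before first dose, with s from 0 to 28 (Appendix 2), the time is -s, that is, -28 to 0 days. This applies only to a patient with no post-baseline scan, no documented progression and no death. The documents do not give the number of such patients. I assume 2% to 15% of a cohort.

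**4. Effect on simple summaries.** The minimum of a range could fall to -28 days. Compared with a time of 0, each such patient lowers a mean by at most 28/n days:

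- B1, n = 50, one patient (2%): 28/50 = 0.56 days
- B2, n = 20, three patients (15%): 3 x 28/20 = 4.2 days

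The separate bias from treating censored times as events cannot be sized, because no event or censoring counts are given.

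**5. Effect on a Kaplan-Meier estimate.** S(t) is the product of (1 - d/r) over event times, where r counts patients whose time is at or beyond that event time. A patient censored on or before Day 1 enters no r, provided the first event falls after Day 1. The curve is therefore unchanged.

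A simulation agrees. It used cohorts of 20, 30, 50 and 100, with 2%, 5%, 10% or 15% having no post-baseline scan (0 to 15 patients after rounding). Assumed median PFS was 3 to 5 months, censoring was uniform over 3 to 18 months, and progression was detected on an 8-week grid. In all 16 scenarios the curve and median were identical whether these patients kept a negative time, were censored at Day 1, or were dropped. Only the listed value and the starting number at risk change.

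**6. Precision of the proposed summary.** With no censoring before 24 weeks and a true 24-week PFS of 50% (an assumption), the 80% half-width is 1.2816 x sqrt(0.25/n):

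- B1, n = 50: 9.1 points
- A, n = 30: 11.7 points
- B2, n = 20: 14.3 points

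These are lower bounds. Censoring would widen them.

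**The case against.** The strongest reply is that this is a matter of wording in an exploratory study. Section 15.1 plans no confirmatory inference. PFS is in no objective. Section 15.2.2 sizes Phase IIa on clinical benefit rate, with response rate for Cohort A, and both are summarised by cohort. Listing a supportive measure is defensible, and Section 15.1 can be read as promising more than a listing. The group affected by the censoring gap is also likely to be small: early progression or death is an event, and Appendix 2 marks CT/MRI and bone scan at end of treatment, waived only if done within 4 weeks.

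Most of that stands and sets the severity. It does not fill the gap, because the statistics Section 15.1 names are unsuitable for censored times.

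A reader might go further and infer that wind-down will leave many patients censored before 24 weeks. The documents do not support this. Section 1.1 reports 107 patients in Phase IIa and Cohort D1 by 9 September 2016, six of them in D1, so 107 - 6 = 101 in Phase IIa against a planned 100. Twenty-four weeks (168 days) from that date is 24 February 2017. Version 9 cites a January 2017 brochure, so it is no earlier than that, and patients with benefit may continue treatment. The 77-day median treatment duration is a preliminary on-treatment figure that combines D1 with Phase IIa. It does not count patients without a scan.

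**Conclusion.** The point holds in a limited form and is minor. Section 15.5 commits to no time-to-event summary of Phase IIa PFS, and Section 15.1 does not supply a valid one. The censoring rule gives about -28 to 0 days for a patient with only a screening scan and no event. That distorts the listing and any simple range or mean, by at most 4.2 days on a mean in the worst case worked above.

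Three stronger readings are tempting but not supported:

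- **That PFS cannot be summarised.** It has a usable time for every patient with an event or a post-baseline scan, and the Kaplan-Meier curve does not depend on how the remaining patients are handled.
- **That the primary objective is left without an analysis.** Response and clinical benefit rates serve it, and PFS is not named in it.
- **That an interval of about 9 points either side in B1 shows a gain over clinical benefit rate.** It is a binomial figure with no censoring, close to Table 13's exact half-width of (59.91 - 40.09)/2 = 9.91 points.

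The conclusion rests on the text of Sections 15.1 and 15.5 and the screening window. The share of patients without a post-baseline scan is an assumption. The Kaplan-Meier invariance assumes no event on or before Day 1.

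**What to change.** In Section 15.5, replace the listing commitment and its undefined qualifier with Kaplan-Meier estimates for Phase IIa Cohorts A (A1 and A2 combined, as Section 15.2.2 sets out), B1 and B2. Give median PFS and 24-week PFS with 80% confidence intervals, matching the level in Table 13, and keep the patient listing. Label the output as descriptive and supportive of response and clinical benefit rates. Add that a patient with no post-baseline assessment and no progression or death is censored at Day 1, and state whether Day 1 is counted as time 0 or 1.

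Separately, the imaging interval needs reconciling because it determines when progression can be dated. The synopsis statistical methods for Phase IIa say scans "will be performed at screening and every 8 weeks from Cycle 1 Day 1 thereafter", while Section 11.1.8 and Appendix 2 defer to institutional guidelines and clinical indication. This review takes no position on which should stand.

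The cost is a few sentences, one table and one figure from data already collected. Intervals will be wide in Cohorts A and B2, and the text should say so.

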## **3. STUDY RATIONALE FOR GDC-0810 AS A SINGLE AGENT AND RISK BENEFIT ASSESSMENT**

GDC-0810 is a small-molecule therapeutic agent that competes with estrogens for binding to the ER with low nanomolar potency. In murine MCF-7 xenograft models, GDC-0810 has demonstrated robust tumor regression in both tamoxifen-sensitive and tamoxifen-resistant models, with superior tumor growth inhibition to fulvestrant at clinically relevant exposures. *In MCF-7 breast cancer cells, the activity of GDC-0810 differentiates from that of first generation ER antagonists, such as tamoxifen, fully antagonizing the response of ER to estrogens and inducing proteosomal degradation of ER $\alpha$ . In other ER+ breast cancer cell lines, such as HCC1500, MDA-MB-330, and Camal cells, GDC-0810 attenuates the transcriptional and proliferative response of ER to estrogens without inducing significant ER $\alpha$  degradation. GDC-0810 has a non-steroidal structure and displays good oral bioavailability in all nonclinical species tested, unlike fulvestrant, which has a steroid structure and exhibits poor bioavailability.*

As of 15 April 2016, a total of 41 patients had been treated with GDC-0810 doses ranging from 100–800 mg. Robust ER target engagement across all doses was demonstrated by FES-PET (fluoroestradiol positron emitting tomography) scans. Sixteen of 41 (39%) evaluable patients in this heavily pre-treated patient population (median 4 prior systemic treatments, range 1–14) had total time on study >6 months, which is comparable to the 24-week clinical benefit rate (CBR) of 32%–42% achieved by fulvestrant in patients with ER+ advanced or metastatic breast cancer (mBC) after one prior endocrine therapy (Chia et al. 2008; Di Leo et al. 2010; Johnston et al. 2013). Additionally, 2 patients with ESR mutations have achieved a partial response by

Response Evaluation Criteria in Solid Tumors (RECIST) 1.1 since the data cut at GDC-0810 doses of 300 mg BID and 400 mg twice daily (BID).

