## 8.2 PHASE IIa

### 8.2.1 Phase IIa Inclusion Criteria

- Histologically or cytologically proven diagnosis of adenocarcinoma of the breast with evidence of either locally recurrent disease not amenable to resection or radiation therapy with curative intent, or metastatic disease, both progressing after at least 6 months of endocrine therapy with an aromatase inhibitor for ER+ breast cancer
- ER-positive tumor (staining in  $\geq$  1% cells by IHC as per local laboratory testing)
- HER2-negative breast cancer as per local laboratory testing (IHC result of 0 or +1 for cellular membrane protein expression or a FISH result showing HER2/CEP17 ratio  $<$  1.8 or an average of fewer than 4 copies of *HER2* gene per nucleus for systems without an internal control probe)

- **Cohort A only:**

Confirmed ESR1 mutations of the LBD (as determined in a Clinical Laboratory Improvement Amendments [CLIA]-certified laboratory) and consent to provide an archival tumor sample for retrospective confirmation (LBD further defined as the region between ER- $\alpha$  amino acids 302 to 595) and

Presence of evaluable disease as per RECIST Version 1 further defined as follows:

Measurable disease, or evaluable bone disease—that is, bone lesions that are lytic or mixed (lytic + sclerotic) in the absence of measurable lesion.

Note: previously irradiated lesions are deemed measurable only if progression is documented at the site after completion of radiation.

- For patients with soft tissue or visceral metastases that are safely accessible, paired pre- and on-treatment tumor biopsies are required.

**Cohort A1 only:** No prior fulvestrant allowed; at least 2 months must have elapsed from the use of tamoxifen (if applicable)

**Cohort A2 only:** Prior fulvestrant allowed

- **Cohort B only:** Disease progression following  $\leq$  1 prior treatment with an AI in the advanced/metastatic setting (prior adjuvant treatment with an AI is allowed):

Patients must have relapsed  $\geq$  12 months from completion of adjuvant treatment or progressed following  $\geq$  6 months of treatment in the advanced/metastatic setting.

Measurable disease, or evaluable bone disease—that is, bone lesions that are lytic or mixed (lytic + sclerotic) in the absence of measurable lesion.

Note: previously irradiated lesions are deemed measurable only if progression is documented at the site after completion of radiation.

**Cohort B1 only:** No prior fulvestrant allowed

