### **15.2.2 Phase IIa**

At the RP2D, a total of approximately 100 patients *have been* enrolled to further assess the safety, tolerability, preliminary evidence of anti-tumor activity, and exploratory PD markers of response of GDC-0810 in 3 distinct patient populations (Cohorts A1 and A2 will be combined for analysis purposes).

A total of 100 patients in Phase IIa will provide a more robust safety profile as well as sample size for preliminary assessment of anti-tumor activity based on clinical benefit rate (CBR) (see [Table 13](#)), defined as the percentage of patients achieving confirmed RECIST v1.1 defined complete response, partial response, and/or stable disease  $\geq 24$  weeks.

In Cohort A, because the presence of ESR1 mutations are associated with poor prognosis, an objective response rate (ORR), defined as the percentage of patients achieving confirmed complete and/or partial responses of at least 15% (5 out of 30 patients) would be considered of more clinical interest than CBR to warrant further development of GDC-0810 in this mutant patient population.

In Cohort B1, the desired observed CBR is 50%, based on historical CBRs of 46% ([Di Leo et al. 2010](#)) and 48% ([Bachelot et al. 2012](#)) for patients with ER+/HER2– advanced breast cancer after prior treatment with aromatase inhibitors.

In Cohort B2, the desired observed CBR is 20%, based on historical CBRs ranging from 18% to 26% for patients with ER+/HER2– advanced breast cancer after prior treatment with fulvestrant ([Baselga et al. 2011](#); [Yardley et al. 2013](#)).

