## **16.4 ARCHIVAL OF DATA**

The database is safeguarded against unauthorized access by established security procedures; appropriate backup copies of the database and related software files will be maintained. Databases are backed up by the database administrator in conjunction with any updates or changes to the database.

At critical junctures of the protocol (e.g., production of interim and final reports), data for analysis are locked and cleaned per established procedures.

An independent radiologic review facility will be used for the purpose of collecting and assessing the quality of patient scans throughout the trial. The review facility will retain copies of scans for centralized assessments of FES-PET and tumor assessment scans.

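### Does Section 15.5 need its own rule for counting clinical benefit in patients with bone disease and no measurable lesion?

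*Combined protocol and SAP*

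**What the plan says.** Section 8.2.1 requires, for Cohorts A and B, either measurable disease or evaluable bone disease, the latter meaning "bone lesions that are lytic or mixed (lytic + sclerotic) in the absence of measurable lesion". Patients with no measurable lesion are therefore in the Phase IIa population by design.

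Section 15.2.2 bases the preliminary assessment of activity on CBR, "defined as the percentage of patients achieving confirmed RECIST v1.1 defined complete response, partial response, and/or stable disease" of 24 weeks or more. Section 15.5 repeats the definition: "CBR is defined as the percentage of patients achieving confirmed RECIST v1.1-defined complete response, partial response, and/or stable disease", again of 24 weeks or more. It also says that objective response and clinical benefit are derived by RECIST v1.1 and summarized by dose level and cohort. Section 11.1.8 also rests response and progression on RECIST v1.1. The non-responder rule in Section 15.5 covers patients with a missing baseline or no response assessment; a bone-only patient with scans is neither. Progression-free survival is to be listed for Phase IIa patients when appropriate.

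Section 15.2.2 then gives the levels of interest. For Cohort A it is an ORR, the "percentage of patients achieving confirmed complete and/or partial responses of at least 15% (5 out of 30 patients"). The next is "In Cohort B1, the desired observed CBR is 50%, based on historical CBRs of 46"% and 48%. For Cohort B2 the level is a CBR of 20%, against historical rates of 18% to 26%. Table 13 attaches two-sided 80% intervals to all three. Section 15.1 says that "no confirmatory inferential analyses are planned".

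**The concern.** Eligibility and endpoint appear not to fit together. If partial response and stable disease could be assigned only where there is a measurable target lesion, a bone-only patient who went 24 weeks without progression would meet none of the three named categories short of complete response. A literal reading would then score her as having no benefit. Anti-tumor activity is the Phase IIa primary objective, and B1 and B2 are read against levels taken from historical CBRs, so a classification rule that moves the rate would also move that comparison.

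Section 3 adds to the impression. It reports that 16 of 41 Phase Ia patients (39%) "had total time on study >6 months, which is comparable to the 24-week clinical benefit rate (CBR") of fulvestrant. Time on study needs no target lesion, so that comparison would credit a bone-only patient who stayed on treatment.

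For Cohort A the worry is a different one. Under the same restrictive reading, bone-only patients stay in the denominator of 30 but could hardly register a partial response. A low ORR could then reflect low activity or simply the mix of disease, and no planned summary separates the two.

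**Working it through.** **Inputs.** Cohort sizes and levels from Section 15.2.2 and Table 13: A, 5/30 ORR; B1, 50% of 50; B2, 20% of 20. The share of patients without a measurable lesion, *f*, is not in the documents; 10 to 40% is assumed throughout as illustration.

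**Step 1: the plan's own figures.** The exact (Clopper-Pearson) 80% interval for *x* of *n* has lower limit equal to the 0.10 quantile of Beta(*x*, *n* − *x* + 1) and upper limit equal to the 0.90 quantile of Beta(*x* + 1, *n* − *x*).

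| Cohort | x/n | Exact 80% interval | Table 13 |
|---|---|---|---|
| A | 5/30 | 8.34–28.74% | 8.34–28.74% |
| B1 | 25/50 | 40.09–59.91% | 40.09–59.91% |
| B2 | 4/20 | 9.02–36.07% | 9.02–36.07% |

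All three agree. The Cohort A row is labelled 15% but uses 5/30 = 16.7%, with all 30 patients in the denominator.

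**Step 2: CBR under the possible rules.** Let *p* be the true 24-week benefit rate, taken as equal with and without measurable disease.

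- Non-progression counts, or the guideline already assigns it to a qualifying category: expected CBR = *p*; no effect.
- It does not count, the patients stay in the denominator and none has a complete response: expected CBR = *p*(1 − *f*), a loss of *p* × *f*.
- The patients leave the denominator: expected CBR = *p*, with a wider interval.

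Under the second rule:

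| f | B1: 50% × (1 − f) | B1 patients reclassified: 50 × f × 0.5 | B2: 20% × (1 − f) | B2 patients reclassified: 20 × f × 0.2 |
|---|---|---|---|---|
| 10% | 45% | 2.5 | 18% | 0.4 |
| 20% | 40% | 5 | 16% | 0.8 |
| 30% | 35% | 7.5 | 14% | 1.2 |
| 40% | 30% | 10 | 12% | 1.6 |

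With 80% intervals, B1 would read 20/50 = 40% (30.6–50.1%) at a 20% share and 15/50 = 30% (21.5–39.8%) at 40%. Under the third rule it would read 20/40 = 50% (38.8–61.2%) and 15/30 = 50% (37.0–63.0%). The planned B1 interval has a half-width of (59.91 − 40.09)/2 = 9.91 points, so a loss of that order needs a share of about 20% as well as the restrictive reading.

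**Step 3: Cohort A.** Suppose 5 responders, all with measurable disease. Over the whole cohort this is 5/30 = 16.7% (8.3–28.7%). Over measurable disease only it is 5/24 = 20.8% (10.5–35.2%) at a 20% bone-only share and 5/18 = 27.8% (14.2–45.5%) at 40%. At the same observed rate of 16.7% the subset is less precise: 4/24 gives 7.47–30.59% and 3/18 gives 6.29–33.44%, widths of 23.1 and 27.2 points against 20.4 for 5/30. Nor could the 15% level be carried over to it. At a true ORR of 10%, P(X ≥ 5 | 30) = 0.175, P(X ≥ 4 | 24) = 0.214 and P(X ≥ 3 | 18) = 0.266, so the smaller denominator makes the level easier to reach by chance.

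**Step 4: which CBR rule do the documents support?** None of these sections describes how RECIST v1.1 treats disease without a measurable lesion; they only refer to it. Every non-zero figure in Step 2 therefore depends on two things that are not in the documents: the restrictive reading and a value of *f*.

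**The case for a change.** The best case for a change is that one sentence would settle the matter whichever reading is right. The result is a primary objective; the bone-only share is not among the summaries the plan names; the progression-free survival listing is conditional; and a reader of Section 15.5 cannot tell from it how these patients were handled. No new scans would be needed, since "The review facility will retain copies of scans for centralized assessments of FES-PET and tumor assessment scans".

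Part of this stands. Section 15.5 does not restate the rule, and a report would be clearer if it gave the rule applied, the number of patients without measurable disease in each cohort, and CBR with and without their 24-week non-progression. Those are reporting choices an analyst can make under the current text.

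The rest does not carry the case:

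- Different classifications by two analysts are possible only if RECIST v1.1 leaves the matter open, and that cannot be shown here.
- Section 3 is background on Phase Ia patients and uses a different measure; it sets no counting rule for Phase IIa.
- Writing into the plan that non-progression counts would not be neutral. The documents do not say how the historical rates of 46%, 48% and 18% to 26% treated such patients, so the change could make the comparison worse as easily as better. With investigator-assessed response in an open-label study, a late definition also invites the question of whether data prompted it.
- Retained scans do not establish that measurable status is captured as a data item.
- For Cohort A, the plan fixes an unambiguous all-patient denominator. Leaving out an extra subset in an exploratory study is a choice, not an error.

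**Conclusion.** No change to the plan. The CBR point is missing detail that the plan covers by reference to RECIST v1.1 and that analysts would fill when deriving response. No stated rule has been shown to give a wrong result. The effect is zero if the guideline assigns bone-only non-progression to a qualifying category. Otherwise it is *p* × *f*: 5 to 20 points in B1 and 2 to 8 points in B2 for an assumed share of 10 to 40%, equal benefit in both groups and no bone-only complete responses. Those ranges are hypothetical.

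The Cohort A point is a preference. The all-patient ORR against 5/30 is a legitimate descriptive quantity; a measurable-disease ORR would rest on fewer patients (18 to 24 at assumed bone-only shares of 40 to 20%) and could only be supportive.

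The stakes are low in either case. The 15%, 50% and 20% levels are descriptive, not tests, so no error rate is affected. Phase IIa enrollment is complete and development of GDC-0810 has been halted, so no go or no-go step in this protocol depends on which side of a level a cohort falls.
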